4.5.6 WHO Functional Class

World Health Organization Functional Class for PH must be documented at Screening (and be in the range 2 to 3) and re-assessed during the study, as outlined in the Schedule of Assessments (see [Appendix 1](#)).

The WHO Functional Class will be performed according to standard guidelines.

4.5.7 GAP Score and Index for IPF

The gender, age and physiology (GAP) score and index for IPF will be automatically calculated based on the information recorded in the eCRF (age, gender, FVC and DLCO).

4.5.8 12-lead Electrocardiograms

Single 12-lead ECG recordings will be obtained at specified timepoints, as outlined in the Schedule of Assessments (see [Appendix 1](#)).

All ECG recordings must be performed using a standard high-quality, high-fidelity digital electrocardiograph machine equipped with computer-based interval measurements. Lead placement should be as consistent as possible.

Patients must have been in a supine or semi-supine position for at least 5 minutes prior to the recording being taken. All ECGs are to be obtained prior to other procedures scheduled at that same time (e.g., vital sign measurements, blood draws) and should not be obtained within 3 hours after any meal. Circumstances that may induce changes in heart rate, including environmental distractions (e.g., television, radio, conversation) should be avoided during the pre-ECG resting period and during ECG recording.

Paper copies of ECG tracings will be kept as part of the patient's permanent study file at the site. The ECG printout must be (1) reviewed by a medically qualified member of the study team at the site, (2) annotated to indicate any clinical finding and (3) dated and signed by this person and filed in the patient notes. ECG parameters will be entered into the eCRF.

If any ECG abnormality is associated with an adverse event, it must be recorded as described in [Section 5.2.1](#).

4.5.9 6-Minute Walk Test and Oxyhemoglobin Saturation

The 6MWT measures the distance that a patient can quickly walk on a flat, hard surface in a period of 6 minutes. Oxyhemoglobin saturation (SpO₂) at rest and during the 6MWT will be assessed at specified timepoints, as outlined in the Schedule of Assessments

(see [Appendix 1](#)). The 6MWT will be performed according to standard procedures ([ATS Statement, 2002](#)) described in the Procedure Manual.

The 6MWT will be performed once for the visits highlighted in the Schedule of Assessments ([Appendix 1](#)). At Day 1, 6MWT will be performed twice and the better of the two 6MWT values will be reported as the baseline value. It is important to remember that for each 6MWT, information on oxyhemoglobin desaturation, Borg scale and O₂ requirements have to be collected.

4.5.10 Transthoracic Doppler ECHO

Transthoracic Doppler ECHO will be assessed at specified timepoints, as outlined in the Schedule of Assessments (see [Appendix 1](#)).

The ECHO procedure will be performed according to standard guidelines ([Galiè et al. 2015](#)).

4.5.11 Spirometry (Post bronchodilator)

Spirometry assessments of FVC, FEV1, and FEV1/FVC ratio will be assessed at specified timepoints, as outlined in the Schedule of Assessments (see [Appendix 1](#)).

Spirometry will be performed only post bronchodilator, approximately 30 minutes after the last puff of short-acting bronchodilator as described in the Procedure Manual. Reference equations for spirometric indices will also be provided in the Procedure Manual.

4.5.12 Diffusing Capacity for Carbon Monoxide

DLCO will be assessed at specified timepoints, as outlined in the Schedule of Assessments (see [Appendix 1](#)).

The reported DLCO will be corrected for the current hemoglobin level, using reference equations.

4.5.13 Health Status and Health-Related Quality of Life

HRQoL will be assessed by SGRQ at selected clinical visits as outlined in the Schedule of Assessments (see [Appendix 1](#)).

4.5.14 UCSD SOBQ

The UCSD SOBQ is a symptom-specific, 24-item, patient-self-administered questionnaire that assesses shortness of breath while doing a variety of activities of daily living. It will be assessed at selected clinical visits as outlined in the Schedule of Assessments (see [Appendix 1](#)).

4.5.15 Patient Study Discontinuation

Patients have the right to voluntarily withdraw from the study at any time for any reason. In addition, the Investigator has the right to withdraw a patient from study at any time. Reasons for withdrawal from the study may include, but are not limited to, the following:

- Patient withdrawal of consent at any time
- Any medical condition that the Investigator or Sponsor determines may jeopardize the patient's safety if he or she continues in the study
- Lung transplantation
- Investigator or Sponsor determines it is in the best interest of the patient

Every attempt should be made to keep patients on study treatment throughout the duration of the trial.

Every effort should be made to obtain information on patients who withdraw from the study. The primary reason for withdrawal from the study should be documented on the appropriate eCRF. However, patients will not be followed for any reason after consent has been withdrawn. Patients who withdraw from the study will not be replaced.

The Investigator should show due diligence and explore all possible options to reach a patient who fails to attend a visit. The site must document all attempts to contact the patient in the medical records / source documents.

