4.2 METHOD OF TREATMENT ASSIGNMENT AND BLINDING

Patients will be randomized 1:1 to receive either pirfenidone plus sildenafil or pirfenidone plus placebo. The randomization process will be conducted using a validated interactive voice or web-based response system (IxRS). To guard against systematic selection bias and ensure comparability of treatment groups, the randomization will be stratified by availability of a previous RHC (yes/no) and by FEV1/FVC ratio below/above 0.8 to ensure an equal distribution of patients with some degree of pulmonary obstruction in both treatment groups.

To maintain the double-blind nature of the study, the sildenafil and placebo treatments will be identical in appearance (see [Section 4.3.1.2](#)).

The investigational site personnel and the patients will be blinded to treatment assignment from randomization onwards. The iDMC and any personnel performing interim analysis (as applicable) will be unblinded to treatment throughout the study.

If unblinding is necessary for patient management (e.g., in the case of a SAE for which patient management might be affected by knowledge of treatment assignment), the Investigator will be able to break the treatment code by contacting the IxRS. Treatment codes should not be broken except in emergency situations. If the Investigator wishes to know the identity of the study drug for any other reason, he or she should contact the Medical Monitor directly. The Investigator should document and provide an explanation for any premature unblinding (e.g., accidental unblinding, unblinding due to a SAE).

For regulatory reporting purposes, and if required by local health authorities, the Sponsor will break the treatment code for all serious, unexpected suspected adverse reactions (see [Section 5.7](#)) that are considered by the Investigator or Sponsor to be related to study drug.

Unblinding should not necessarily result in the withdrawal of a patient from the study. Every effort should be made to retain unblinded patients in the study.

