4.5.16 Patient Study Treatment Discontinuation

Patients must discontinue study treatment (sildenafil and/or pirfenidone) if they experience any of the following (see also [Sections 5.1.1](#) and [5.1.2](#)):

- Inability to tolerate study treatment after efforts have been made to gain tolerability
- An elevation in liver test results of the magnitude described below
- Use of a prohibited investigational therapy or concomitant medication
- Sildenafil/placebo will be stopped in patients with acute coronary syndromes, atrioventricular AV block, life-threatening arrhythmias, left ventricular dysfunction (ejection fraction <25%), or clinically significant visual changes
- Pregnancy
- Signs or symptoms of angioedema
- Any other treatment-emergent adverse event or toxicity that is unacceptable in the opinion of the patient or Investigator

Sildenafil/placebo will be stopped (temporarily or permanently) in any patient with systolic blood pressure (SBP) <100 mmHg or diastolic blood pressure (DBP) <50 mmHg.

The primary reason for study treatment discontinuation should be documented on the appropriate eCRF. Patients who discontinue study treatment prematurely will not be replaced.

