6.1 DETERMINATION OF SAMPLE SIZE

There are no reference data available on the use of pirfenidone in this patient population with a measurable DLCO \leq 40% of predicated value and mPAP \geq 20 mmHg on RHC. A total sample size of approximately 176 patients is planned, and patients will be randomized 1:1 to the two treatment groups. The statistical hypothesis for the treatment comparison is based on the proportion of patients who experienced a \geq 15% decline from baseline in 6MWD, were hospitalized for cardiac- or respiratory non-elective reasons, or who died, according to a pooled analysis of the effects observed in the pirfenidone groups of three large Phase III trials (CAPACITY 1, CAPACITY 2, and ASCEND).

The planned sample size is based on the primary endpoint, proportion of patients with disease progression and assumes 80% power and a one-sided significance level of 5%. Given the disease progression rate of 72% by 52 weeks in the three large registration trials for pirfenidone, and assuming an additive effect of sildenafil on pirfenidone, a disease progression rate of 54% in the combination treatment group is assumed and an absolute difference of 18% (respectively a relative reduction of 25%) in disease progression rates is considered a clinically meaningful treatment benefit.

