6.4 EFFICACY ANALYSES

The primary and secondary efficacy analyses will include all randomized patients, with patients grouped according to their assigned treatment.

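### Section 4.5.15 allows study withdrawal on safety or best-interest grounds without withdrawn consent, and no procedure secures deaths and hospitalisations to Week 52 for these patients

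*Protocol*

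**What the plan says.** **Leaving the study.** Protocol Section 4.5.15 gives the Investigator a right to withdraw a patient from the study whenever he or she chooses. It then gives an open-ended list of reasons. Two rest on a judgement by the Investigator or Sponsor: "Any medical condition that the Investigator or Sponsor determines may jeopardize" the patient's safety, and the patient's best interest. The same section asks sites to make an effort to obtain information on patients who leave. The one explicit bar is that "patients will not be followed for any reason after consent has been withdrawn".

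**Stopping drug.** Section 4.5.16 has its own list for stopping sildenafil/placebo or pirfenidone, including "Any other treatment-emergent adverse event or toxicity that is unacceptable in the opinion of the patient or Investigator". It does not say that these patients remain in follow-up to Week 52.

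**Staying in.** Section 3.1 encourages patients with a non-fatal primary event to complete the study. Section 4.2 says of another group that "Every effort should be made to retain unblinded patients in the study".

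**Collection.** Sections 5.3.1, 5.3.5.7 and 5.4.2.2 collect adverse events, deaths and serious adverse events until 28 days after the last dose. After that, Section 5.6 asks only for serious events believed related to study drug. Appendix 1 has one shared column for early study withdrawal and treatment discontinuation.

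**Analysis.** Section 6.4 states that "The primary and secondary efficacy analyses will include all randomized patients". Section 6.4.1 counts relevant 6MWD decline, respiratory non-elective hospitalisation and all-cause death over 52 weeks, on available data and without imputation.

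**The concern.** A safety judgement is a reason to stop a drug, or to spare a patient a walk test. It is not a reason to stop recording whether the patient is alive or has been admitted. Section 4.5.15 does not separate the two, so a patient who has not withdrawn consent can leave the study on someone else's decision. The protocol then has no step that records the death or hospitalisation the primary endpoint needs.

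Such withdrawals are plausibly informative. A patient judged unsafe to continue is probably at higher risk than average. Sildenafil also has stopping reasons of its own in Section 4.5.16, such as low blood pressure and visual changes, so withdrawals could differ by arm. Both are inferences; the protocol states neither. If both hold, unrecorded events would favour the arm with more safety withdrawals, in efficacy and in mortality. Mortality matters here because Section 1.3 explains the safety plan by a related trial stopped for a possible excess of deaths.

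**Working it through.** **Inputs from Section 6.1.** The calculation "assumes 80% power and a one-sided significance level of 5" per cent. For the control rate: "Given the disease progression rate of 72% by 52 weeks". For the sildenafil arm: "a disease progression rate of 54% in the combination treatment group is assumed". About 176 patients are randomised 1:1, so 88 per arm.

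**Formula.** One-sided two-proportion test with pooled variance and no continuity correction. Let *d* be the control rate minus the sildenafil rate, SE0 the pooled standard error and SE1 the unpooled one. Then P(reject) = Φ((*d* − 1.645·SE0)/SE1).

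**1. The plan's own figure.** The pooled rate is 0.63.
- n = [1.645·√(2×0.63×0.37) + 0.842·√(0.72×0.28 + 0.54×0.46)]² / 0.18² = 87.9, so 88 per arm and 176 in total. This reproduces the plan.
- Power at 88 per arm: SE0 = 0.0728, SE1 = 0.0715, (0.18 − 0.1197)/0.0715 = 0.843, giving 80.0%.

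Nothing is left over for dropout, and Section 4.5.15 does not replace withdrawn patients.

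**2. Power if 10% of each arm is withdrawn at that arm's average risk (assumed).**
- Excluded: 79.2 per arm, 72% v 54%. SE0 = 0.0767, SE1 = 0.0754, (0.18 − 0.1262)/0.0754 = 0.714, giving 76.2%.
- Scored as non-events: 0.9×72% = 64.8% v 0.9×54% = 48.6%, 88 per arm. SE0 = 0.0747, SE1 = 0.0737, (0.162 − 0.1229)/0.0737 = 0.531, giving 70.2%.

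**3. False-positive rate with no true effect.** The true rate is 72% in both arms; 10% of sildenafil and 5% of placebo patients are removed before an event (assumed).

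| Scoring of those removed | Their risk | Placebo v sildenafil | P(reject), nominal 5% |
|---|---|---|---|
| Excluded | Average | 72.0% v 72.0% | 5.0% |
| Excluded | All would have progressed | 0.67/0.95 = 70.5% v 0.62/0.90 = 68.9% | about 8% |
| Non-events | Average | 0.95×72% = 68.4% v 0.90×72% = 64.8% | about 13% |
| Non-events | All would have progressed | 72−5 = 67% v 72−10 = 62% | about 17% |

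For the last row, SE0 = 0.0721, SE1 = 0.0720 and (0.05 − 0.1187)/0.0720 = −0.953, giving 17.0%. If half of the lost events in that row were recovered, the rates would be 69.5% v 67.0% and P(reject) about 10%.

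**4. The collection rules together.** Take a patient withdrawn on safety grounds at Week 20, who takes the last dose then and dies or is admitted for a respiratory cause at Week 35. The event falls inside the 52-week endpoint. It is outside the 28-day window, is not reportable under Section 5.6 unless believed drug-related, and matches no later assessment in Appendix 1. Whether it is recorded depends on the general request for effort in Section 4.5.15.

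**The case against.** Section 4.5.15 answers part of this itself. A reader might infer that follow-up for death and hospitalisation ends for these patients. The text does not say so: it asks for information on everyone who withdraws and bars follow-up only after consent is withdrawn. That objection stands. What remains is that the request has no procedure behind it.

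A reader might also infer that stopping drug amounts to leaving the study. Section 4.5.16 is a separate list and does not say that, so a drug reaction would normally be handled there. The grounds in 4.5.15 are permissive. Continuing in the study also means walk tests and lung function tests, so a safety ground is not empty. This supports a right to stop procedures, but not the loss of vital status.

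Patients who already had a qualifying event count whether or not they leave later. That limits the loss to withdrawals before an event.

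The sharpest objection concerns size. A reader might take 17% as the expected false-positive rate. It requires every removed patient to be scored as a non-event, every one to have been going to progress, and no event to be recovered. Section 6.4.1 does not fix that scoring, and with exclusion at average risk there is no inflation. The 10% v 5% imbalance is also assumed.

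Sensitivity analyses are left to the SAP, which is not at hand. They may address scoring, but they cannot supply events that were never collected. Finally, ending follow-up at consent withdrawal respects the patient's decision and is not an error. Any use of public records depends on local law and on consent text that is not available here.

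**Conclusion.** The point holds as a gap in follow-up: study withdrawal on safety or best-interest grounds is permitted without withdrawn consent, and nothing defined secures deaths and respiratory hospitalisations to Week 52 for these patients. The documents do not show that such data will be lost, only that they may be.

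The size rests on assumed withdrawal rates, because the protocol gives none. At 10% per arm and average risk, the cost is about 4 points of power under exclusion and about 10 points under non-event scoring. At 10% v 5% with no true effect, the false-positive rate lies between 5% and about 17%. Larger imbalances would give larger rates, but nothing in the protocol supports choosing one. Without a dropout allowance, any loss of this kind comes straight out of the planned 80%. The change is worth making because it is cheap and the missing events cannot be recovered at analysis.

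**What to change.** - **Section 4.5.15, grounds.** Make the medical-condition and best-interest grounds reasons to stop study treatment and on-site procedures, not to leave the study.
- **Section 4.5.15, general wording.** Amend the Investigator's unrestricted right to withdraw a patient from the study, and close the open-ended list, to match. Otherwise removing the two grounds changes nothing.
- **Sections 4.5.15 and 4.5.16.** State that all randomised patients who have not withdrawn consent are followed to Week 52. Use visits where feasible, and otherwise contact for vital status and non-elective hospitalisation, whatever the time since the last dose.
- **Sections 5.3.1, 5.3.5.7 and 5.6, and Appendix 1.** Align them with this rule, and separate treatment discontinuation from study withdrawal in the schedule.
- **At consent withdrawal.** Ask whether vital-status follow-up may continue, where local law allows.

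Lung transplantation has its own withdrawal rule in Section 6.4.1 and is not changed here.

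The cost is protocol and consent wording and a few site contacts per patient. The sample size stays at 176, and no clinical stopping rule changes.

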4.5.16 Patient Study Treatment Discontinuation

Patients must discontinue study treatment (sildenafil and/or pirfenidone) if they experience any of the following (see also [Sections 5.1.1](#) and [5.1.2](#)):

- Inability to tolerate study treatment after efforts have been made to gain tolerability
- An elevation in liver test results of the magnitude described below
- Use of a prohibited investigational therapy or concomitant medication
- Sildenafil/placebo will be stopped in patients with acute coronary syndromes, atrioventricular AV block, life-threatening arrhythmias, left ventricular dysfunction (ejection fraction <25%), or clinically significant visual changes
- Pregnancy
- Signs or symptoms of angioedema
- Any other treatment-emergent adverse event or toxicity that is unacceptable in the opinion of the patient or Investigator

Sildenafil/placebo will be stopped (temporarily or permanently) in any patient with systolic blood pressure (SBP) <100 mmHg or diastolic blood pressure (DBP) <50 mmHg.

The primary reason for study treatment discontinuation should be documented on the appropriate eCRF. Patients who discontinue study treatment prematurely will not be replaced.

4.5.17 Study and Site Discontinuation

The Sponsor has the right to terminate this study at any time. Reasons for terminating the study may include, but are not limited to, the following:

- The incidence or severity of adverse events in this or other studies indicates a potential health hazard to patients.
- Patient enrollment is unsatisfactory.

The Sponsor will notify the Investigator if the Sponsor decides to discontinue the study.

The Sponsor has the right to close a site at any time. Reasons for closing a site may include, but are not limited to, the following:

- Excessively slow recruitment
- Poor protocol adherence
- Inaccurate or incomplete data recording
- Non-compliance with the International Conference on Harmonisation (ICH) guideline for Good Clinical Practice
- No study activity (i.e., all patients have completed the study and all obligations have been fulfilled)

5. ASSESSMENT OF SAFETY

5.1 SAFETY PLAN

Pirfenidone and sildenafil are both approved treatments and all safety information is contained in their respective EU SPCs and US prescribing information. For this study, the Reference Safety Information (RSI) for pirfenidone is the Investigator Brochure (I.B.). For this study, the Reference Safety Information (RSI) for sildenafil is the US Prescribing Information.

<https://dailymed.nlm.nih.gov/dailymed/drugInfo.cfm?setid=2582414d-0ef3-403e-84e8-1d6c812e7eb1>

Several measures will be taken to ensure the safety of patients participating in this study. Eligibility criteria have been designed to exclude patients at higher risk for toxicities. Patients will undergo safety monitoring during the study, including assessment of the nature, frequency, and severity of adverse events. In addition, guidelines for managing adverse events, including criteria for dosage modification and treatment interruption or discontinuation, are provided below. Safety-related interim analyses will be performed, including hospitalizations and all-cause mortality, and the data assessed by the iDMC (see [Section 3.1](#)). All procedures are detailed in the Schedule of Assessments ([Appendix 1](#)).

5.1.1 Risks Associated with Pirfenidone

5.1.1.1 Impaired Hepatic Function

Elevations in ALT and AST $>3 \times$ ULN have been reported in patients receiving therapy with pirfenidone. These have rarely been associated with concomitant elevations in bilirubin. Liver function tests (ALT, AST and bilirubin) will be conducted at Screening and Day 1 prior to the initiation of study treatment and subsequently at each clinic visit during the study. In the event of significant elevation of liver aminotransferases, the dose of pirfenidone should be adjusted or treatment discontinued according to the guidelines listed in [Table 3](#).

Table 3 Management of Dosing in Patients with Elevated Aminotransferase Test Results

Management or Elevation in ALT or AST	Recommendation
> 3 to $< 5 \times$ ULN without hyperbilirubinemia	Discontinue confounding medications Monitor the patient closely, including repeat liver chemistry tests. Maintain the daily dose at full dose, if clinically appropriate, or reduce or interrupt the dose (e.g., until liver chemistry test results are within normal limits) with subsequent re-titration to full dose as tolerated.
> 3 to $< 5 \times$ ULN with symptoms or hyperbilirubinemia	Discontinue pirfenidone and the patient should not be rechallenged
$> 5 \times$ ULN	Discontinue pirfenidone and the patients should not be rechallenged.

ALT = alanine aminotransferase; AST = aspartate aminotransferase; ULN = upper limit of normal

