4.3.2.6 Restarting Study Treatment

After a treatment interruption, study treatment can be restarted, at the discretion of the Investigator. The schedule for pirfenidone re-titration according to the label, is described in [Table 2](#).

Table 2 Schedule for Pirfenidone Re-titration After an Interruption of More Than 14 Consecutive Days

Day (relative to restart of pirfenidone treatment)	Pirfenidone dosage (as tolerated)
Days 1 to 7	1 capsule TID, with food
Days 8 to 14	2 capsules TID, with food
Day 15 onwards	3 capsules TID, with food

TID = three times daily

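### Table 3's first row does not exclude symptoms, so a symptomatic patient with ALT/AST >3 to <5 × ULN and normal bilirubin falls under two conflicting pirfenidone dosing rules

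*Protocol*

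**What the plan says.** Protocol Section 5.1.1.1 directs that pirfenidone be adjusted or stopped according to Table 3 when liver aminotransferases are significantly raised. Two rows of that table share the range ALT or AST >3 to <5 × ULN:

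- **Row 1**, "ULN without hyperbilirubinemia": stop confounding medications, monitor closely and repeat liver tests. On dose: "Maintain the daily dose at full dose, if clinically appropriate, or reduce or interrupt the dose", "with subsequent re-titration to full dose as tolerated".
- **Row 2**, "ULN with symptoms or hyperbilirubinemia": "Discontinue pirfenidone and the patient should not be rechallenged".

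Two other sections bear on the same decision. Section 4.5.16 opens its list of stopping conditions with "Patients must discontinue study treatment (sildenafil and/or pirfenidone) if they experience any of the following", and one item on that list is "An elevation in liver test results of the magnitude described below". Section 4.3.2.6 states: "After a treatment interruption, study treatment can be restarted, at the discretion of the Investigator".

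**The concern.** Row 2 is entered by either of two conditions, symptoms or raised bilirubin. Row 1 should be its complement, but it excludes only raised bilirubin. A patient with symptoms and normal bilirubin is therefore described by both rows. One lets the site continue or re-titrate; the other takes the patient off pirfenidone for good.

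This is an operative hepatic dosing rule, and the overlap may not be marginal within row 2. Section 5.1.1.1 itself describes accompanying bilirubin elevations as rare, so symptoms with normal bilirubin could be the more usual way into that row. Table 3 does not define symptoms. Sections 5.1.1.3 and 5.1.1.6 list nausea, vomiting, abdominal pain and fatigue among pirfenidone's known effects. A site seeing nausea with ALT at 4 × ULN and normal bilirubin could follow row 1 in good faith.

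If it did, a patient whom row 2 would stop permanently could stay on drug or be rechallenged. Once the site has treated the episode as an interruption, Section 4.3.2.6 supports a restart at its discretion, which row 2 rules out.

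**Working it through.** No power, alpha or sample-size figure is involved. The check is whether the two rows divide the range >3 to <5 × ULN cleanly.

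**Conditions as printed**

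- Row 1 applies if there is no hyperbilirubinemia.
- Row 2 applies if there are symptoms, or hyperbilirubinemia, or both.

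**All four combinations within the range**

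| Symptoms | Hyperbilirubinemia | Row 1 met | Row 2 met | Result |
|---|---|---|---|---|
| No | No | Yes | No | Row 1 only |
| Yes | No | Yes | Yes | **Both rows, conflicting actions** |
| No | Yes | No | Yes | Row 2 only |
| Yes | Yes | No | Yes | Row 2 only |

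One of the four cells overlaps. With row 1 reworded to exclude symptoms as well, the second line meets row 2 only and the overlap falls from 1 of 4 to 0 of 4.

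**Does another part of the protocol decide the overlapping cell?**

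- Section 4.5.16 refers to the magnitude of the liver elevation. That magnitude is the same in both rows, so the wording does not choose between them, although its mandatory tone favours stopping.
- Section 4.3.2.6 is a general restart permission and sets no liver condition.
- Section 5.1.3 refers to the product labels and states no rule of its own.
- Sections 5.2.3 and 5.3.5.6 set the 24 h liver reporting trigger. It needs raised bilirubin or clinical jaundice alongside the aminotransferase elevation, so a patient with neither does not meet it. It is in any case a reporting rule, not a dosing rule.
- Section 5.3.5.4 makes a laboratory abnormality with clinical symptoms a reportable adverse event, but attaches no dosing action.
- Section 4.3.2.5 and the last item of the Section 4.5.16 list leave the matter to general judgement about toxicity.

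Table 3 is thus the only dosing rule with a liver threshold that covers this patient, and it gives two answers.

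**How many patients could be involved**

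The protocol gives no frequency for elevations in this range. Assuming that 1% to 5% of the approximately 176 patients reach it:

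- 176 × 0.01 = 1.76, about 2 patients
- 176 × 0.05 = 8.8, about 9 patients

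These counts are for the whole >3 to <5 × ULN group. The symptomatic subset with normal bilirubin is smaller and cannot be computed from the document.

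**The case against.** The strongest reply is that the intended reading is clear. Row 2 names symptoms explicitly; if row 1 governed symptomatic patients, that part of row 2 would do no work. Section 4.5.16 makes discontinuation mandatory once any listed condition is met, and row 1 does not cancel it. On this view a site that follows row 1 has misread the table. This stands as evidence of intent: a careful reader would probably stop the drug. It does not remove the overlap, because no footnote or precedence statement says that row 2 prevails.

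Row 1 is also not lax. It keeps full dose only where clinically appropriate and requires close monitoring with repeat tests. Liver tests are done at every clinic visit, a symptomatic laboratory abnormality must be reported as an adverse event, and the Medical Monitor can be consulted. All of this is true and limits the harm. None of it supplies row 2's bar on rechallenge.

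The number affected is likely to be small. Entry excludes ALT or AST above 1.5 × ULN and any bilirubin above ULN. Patients need at least 12 weeks of prior pirfenidone, with no related event of Grade 2 or higher in the 4 weeks before Screening. Section 1.2.1 reports that elevations typically arose in the first 6 months of treatment and were generally transient and reversible. These points are fair and are a reason to rank this low.

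The Section 4.3.2.6 argument is secondary. That sentence adds no conflict of its own and matters only once row 1 has been chosen.

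**Conclusion.** The point holds as a defect in the printed rule. Within ALT/AST >3 to <5 × ULN, the combination of symptoms and normal bilirubin meets two rows with incompatible actions, and nothing in the protocol expressly says which governs. The difference at stake is a permanent stop without rechallenge against a discretionary range from full dose to interruption with re-titration.

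Its weight is minor. Stopping is probably what was meant, few patients are likely to be affected, and power and the primary test are unaffected. The overlap itself follows from the wording of the table and rests on no assumption; only the patient count rests on the assumed 1% to 5%. It is still worth correcting, because the table applies to both arms at approximately 75 centers and a hepatic stopping rule should not depend on each site inferring which row prevails.

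**What to change.** Reword the condition in row 1 of Table 3 to: >3 to <5 × ULN without symptoms or hyperbilirubinemia. Row 2 then alone governs symptomatic patients, and every combination in the range has exactly one action.

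As an optional tidy-up, if the printed table does show >5 × ULN in row 3, change it to ≥5 × ULN. A value of exactly 5 × ULN currently falls in no row.

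The cost is two added words and, optionally, one inequality sign. Data collection, sample size and analysis do not change.
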